9.0 TREATMENT/INTERVENTION PLAN

Erlotinib will be commercially obtained. Investigators should reference the current approved prescribing information. A pill diary will be used to track adherence. Erlotinib is administered daily, at approximately the same time of day every day. Erlotinib should be taken on an empty stomach (at least 1 hour before, or 2 hours after the ingestion of food). If vomiting occurs during the course of treatment, patients should not take an additional dose of erlotinib that day. The patient should resume treatment with the next scheduled dose. If more than 12 hours have elapsed, that day's dose should be omitted, and the patients should continue treatment with the next scheduled dose. A pill diary will be used to record adherence.

9.1.2 Therapeutic Agent-Trametinib

Trametinib will be supplied for the purposes of this trial by Novartis. Trametinib is given once daily and can be taken with or without food at approximately the same time of the day each day. A pill diary will be used to record adherence.

9.2 Treatment Arms

All patients will receive trametinib and erlotinib in this single-arm study.

9.3 Study design

Phase 1 (safety run-in): This portion of the study will assess whether a dose of trametinib 1.5mg by mouth once daily and erlotinib 75mg by mouth once daily is a safe dose. Six patients will need to be enrolled at this dose level and assessed for dose limiting toxicities (DLTs) for 1 full cycle (28 days). Toxicity will be graded according to NCI CTCAE version 4.0. If more than one patient develops a DLT, we will move on to the phase 2 portion of the study and the dose level -1 will be used. Dose level -1 of trametinib 1mg daily and erlotinib 100mg daily was already established to be safe and tolerable in a previous phase 1 study. If ≤ 1 DLTs are detected, we will move on to the phase 2 portion of the study at dose level 0.

Dose levels	Trametinib Dose	Erlotinib Dose
Dose Level 0	1.5mg PO qdaily	75mg PO qdaily
Dose Level -1	1 mg PO qdaily	100mg PO qdaily

Phase 2: All patients will receive erlotinib and trametinib at the dose level defined during the phase 1 portion of the study. Patients will be monitored for response by CT every 2 cycles (8 weeks). The first 8 week response will be considered the primary objective outcome for this portion of the study. The schedule of evaluations and interventions is described in Section 10.0.

9.4 Dose Limiting Toxicities:

The NCI Common Terminology Criteria for Adverse Events Version 4.0 (NCI CTCAE) will be used to grade toxicities during the trial. Dose limiting toxicities (DLTs) are defined as any of the following events occurring during the first cycles of treatment (i.e. 4 weeks) that are, in the opinion of the treatment physician, possibly, probably, or definitely related to the investigational regimen:

- Death related to the investigational regimen
- Hematologic toxicities including:
 - Grade=4 neutropenia lasting >5 days
 - Grade=4 thrombocytopenia (<25,000/mm³)
 - Grade \geq thrombocytopenia with evidence of clinically significant bleeding
 - Grade=4 anemia
- Non-hematologic toxicities include:
 - Grade \geq 3 AST, ALT, alkaline phosphatase or total bilirubin
 - Grade \geq 3 diarrhea, nausea, vomiting that lasts >72 hours despite optimal maximum supportive care
 - Grade 4 diarrhea, nausea, vomiting
 - Any other non-hematologic grade \geq 3 major organ toxicity
 - central serous retinopathy or retinal vein occlusion

9.5 Correlative Studies: Biopsies will be required prior to start of study treatment and at the time of progression. At prespecified time points, and after additional informed consent, patients will

have image-guided core needle biopsies with 3-4 cores obtained. At least 2 cores will be immediately frozen in liquid nitrogen and sent to [name] lab.

The remaining cores will be fixed in formalin and sent to Surgical Pathology. Blood will also be used for IMPACT testing for next-generation sequencing based testing if not obtained previously.

DNA/RNA will be extracted from one flash-frozen core using an AllPrep® DNA/RNA mini kit (Qiagen). RNA quality will be assessed at the MSKCC integrative genomics (iGO) core facility using an Agilent Bioanalyzer 2100 platform. We will perform RNA-seq on all patients with sufficient tissue from the phase 2 cohort, to quantify changes in gene expression at various time points of treatment and to identify potential biomarkers of response to combination therapy. Extracted RNA (5ug) will be submitted to Genewiz for single-end 75bp reads on a HiSeq 2500 instrument. RNA samples that are limiting in quality/amount will be amplified using the Ovation® RNA-seq System V2 kit (NuGen) and submitted for RNA-seq as cDNA. We expect RNA yields from core biopsies to be limiting, thus we will not perform rRNA depletion prior to submission of samples. Analysis of RNA-seq data will be performed at the MSKCC Bioinformatics core facility. Remaining RNA will be frozen at -80C for validation of genes of interest highlighted by RNA-seq data. Validation will be performed using either RT-PCR or through the construction of a custom nanostring nCounter panel that includes genes of interest. One fixed core will be used for immunohistochemistry to determine protein expression for transcripts of interest, including: BIM, cleaved caspase 3, TGFB2, vimentin, e-cadherin, n-cadherin and neurofibromin. MSK-IMPACT, our next-generation sequencing based mutation platform that assesses for genetic alterations in 340 cancer-related genes will be used for molecular analysis.

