1.0 PROTOCOL SUMMARY AND/OR SCHEMA

Study Title:	A Phase 1/2 Trial of Trametinib and Erlotinib in Patients with EGFR-Mutant Lung Adenocarcinomas and Acquired Resistance to Erlotinib
Study Objectives:	
Phase 1: Safety Run In
 
Primary Objective: Determine the safety and tolerability of erlotinib 75mg by mouth once daily with trametinib 1.5mg by mouth once daily for patients with acquired resistance to erlotinib
 
Phase 2:
 
Primary Objective: Assess overall response rate (CR+PR) of trametinib when given in combination with erlotinib for patients with EGFR-mutant lung cancers and acquired resistance to erlotinib
 
Secondary Objectives: 1) Measure progression-free survival and overall survival among patients treated with trametinib and erlotinib 2) further define the toxicity profile of the combination
 
Correlative Studies:
 
Objectives: 1) Confirm BIM induction with MEK inhibition by assessing BIM protein expression by IHC on serial biopsies 2) Identify changes in protein expression related to apoptosis, EMT and NF1 expression 3) Perform transcriptome analysis (using RNA-seq) on tumor tissue from serial biopsies. 4) Perform next-generation sequencing based mutation testing to identify genetic alterations on tumor tissue from serial biopsies 5) Assess EGFR T790M status on all patients on study.

Patient Population:	Patients with locally advanced or metastatic lung adenocarcinomas with a confirmed EGFR mutation who have developed acquired resistance to EGFR tyrosine kinase inhibitor therapy
Number of patients:	
Phase 1: Maximum of 6 patients
 
Phase 2: Maximum of 24 patients (including up to 6 patients from Phase 1)

Inclusion Criteria:	
All patients must have:
 
 • Pathologic evidence of stage IV or recurrent lung adenocarcinoma that cannot be treated with curative intent • Somatic activating mutation in EGFR • Radiographic progression during treatment with erlotinib. Prior chemotherapy regimens are permitted. • Measurable (RECIST 1.1) indicator lesion not previously irradiated

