2.1 OBJECTIVES AND SCIENTIFIC AIMS

Hypothesis: The combination of erlotinib and trametinib is an effective treatment in patients with EGFR mutant lung cancers with acquired resistance to erlotinib monotherapy.

Phase 1 Trial:

- A. Primary Objective: Determine the safety and tolerability of erlotinib 75mg by mouth once daily with trametinib 1.5mg by mouth once daily

Phase 2 Trial:

- A. Primary Objectives: Assess overall response rate (CR+PR) of trametinib when given in combination with erlotinib in patients with acquired resistance to erlotinib at 8 weeks (2 cycles)
- B. Secondary Objective: Measure progression free survival and overall survival among patients treated with trametinib and erlotinib and further define the toxicity profile of the combination

[figure not shown]
Correlative Studies:

- A. Primary Objective: 1) Determine whether trametinib leads to upregulation of BIM in patients with acquired resistance 2) Identify changes in protein expression related to apoptosis, EMT and NF1 expression 3) Perform transcriptome analysis (using RNA-seq) on tumor tissue from serial biopsies. 4) Perform next-generation sequencing based mutation platform testing to identify genetic alterations on tumor tissue from serial biopsies

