14.0 BIOSTATISTICS

Phase 1: Safety Run In

Primary Objective: To determine the safety and tolerability of the combination of erlotinib 75mg by mouth once daily with trametinib 1.5mg by mouth once daily in patients with EGFR mutant lung cancer and acquired resistance to EGFR tyrosine kinase inhibitors.

Endpoints: Identify any dose limiting toxicities of the combination. A dose limiting toxicity is a binary

outcome where a patient either experiences a DLT or not. DLT is defined as any of the toxicities described in Section 9 that occurs within one cycle after initiation of treatment with erlotinib and trametinib.

Method: Up to six patients will be enrolled at dose level 0 (trametinib 1.5mg by mouth once daily and erlotinib 75mg by mouth once daily) and assessed for dose limiting toxicities (DLTs) for 1 full cycle (28 days). Toxicity will be graded according to NCI CTCAE version 4.0. If more than one patient develops a DLT, we will move on to the phase 2 portion of the study and the dose level -1 will be used. If ≤ 1 DLTs are detected, we will move on to the phase 2 portion of the study at dose level 0.

If 0-1 DLTs occur, and dose level 0 is used in the phase 2, the patients accrued during the phase 1 portion of the study will be followed for response assessment and included in the phase 2 portion of the study. Given an expected accrual rate of 2 patients per month, the accrual to the phase 1 portion of the study will be completed in about 3 months. Two to six patients will be enrolled in the phase 1 portion of the study.

Dose levels	Trametinib Dose	Erlotinib Dose
Dose Level 0	1.5mg PO qdaily	75mg PO qdaily
Dose Level -1	1 mg PO qdaily	100mg PO qdaily

Phase 2:

Primary Objective: To determine the ORR of the combination of erlotinib and trametinib in patients with EGFR mutant lung cancer and acquired resistance to EGFR tyrosine kinase inhibitors

Secondary Objective: To determine the progression free survival and overall survival and further assess the toxicity of trametinib and erlotinib

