Methods: A Simon optimal two-stage trial design will be utilized to assess the primary endpoint of response rate (RECIST 1.1 CR+PR). This study will test the null hypothesis of 5% response rate against the alternative hypothesis of 25% response rate for patients with acquired resistance. A null hypothesis of 5% was chosen because all eligible patients have demonstrated progression and lack of response to erlotinib. The most effective treatment for both EGFR T790M positive and negative patients is afatinib and cetuximab which has a response rate of 29% but results in significant adverse events¹⁸. Subsequently, an alternative hypothesis of 25% was chosen for this study. The design chosen has a 10% type I error (falsely accepting a non-promising therapy), 10% type II error (falsely rejecting a promising therapy), for 90% power. In the first stage of this design, 9 patients will be treated. If 0 responses are seen in the first 9 patients, the trial will be stopped and declared negative. If at least 1 response is observed, than an additional 15 patients will be accrued to the second stage. At the end of the study, if 3 or more patients have a response out of a total of 24 patients enrolled, the combination of trametinib and erlotinib will be considered worthy of further investigation. Overall survival and time to progression will be estimated using the Kaplan-Meier method, with the follow-up starting at the initiation of therapy. Patients will be censored at the time of the last on-study evaluation if they do not experience the event of interest. Safety and tolerability will be summarized using descriptive statistics. The toxicities and the adverse events will be assessed for each patient according to the NCI CTCAE version 4.0 criteria. All correlative aims are exploratory and will be hypothesis-generating only.

Given an expected accrual rate of 2 patients per month, the accrual to the phase 2 portion of the study will be completed in about 6-12 months.

Correlatives: For the correlative studies, the analysis is primarily exploratory and hypothesis generating. Correlative studies will be performed on all patients participating in both the phase 1 and 2 portions of this clinical trial.

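### Does the missing 8-week time point in Section 14 leave it unclear which responses count toward the 0/9 and 3/24 rules?

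*Combined protocol and SAP*

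**What the plan says.** Two sections give the phase 2 primary outcome a time point. Section 2.1 sets the primary objective as the rate of CR plus PR "in patients with acquired resistance to erlotinib at 8 weeks (2 cycles"). Section 9.3 says: "The first 8 week response will be considered the primary objective outcome for this portion of the study".

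Three places leave the time point out:
- the synopsis in Section 1.0: "Assess overall response rate (CR+PR) of trametinib when given in combination with erlotinib for patients with EGFR-mutant lung cancers";
- the phase 2 objective in Section 14.0: "To determine the ORR of the combination of erlotinib and trametinib in patients with EGFR mutant lung cancer";
- the methods paragraph in Section 14.0: "A Simon optimal two-stage trial design will be utilized to assess the primary endpoint of response rate (RECIST 1.1 CR+PR").

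Section 14.0 also holds the decision rules. At stage 1, "If 0 responses are seen in the first 9 patients, the trial will be stopped and declared negative". At the end, three or more responders among 24 count as success. The 25% alternative is set with an eye to "afatinib and cetuximab which has a response rate of 29% but results in significant adverse events", and no time point is attached to that rate.

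Section 12.0 defines best overall response as the best category reached between the start of treatment and progression, and it does not require confirmation. The scan window is one week either side in Section 12.0 and two weeks either side in footnote 6 of Table 10.1.

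**The concern.** The section with the hypotheses and both decision rules is the one an analyst will open first, and it does not say when response is read. Imaging goes on every 8 weeks, so a patient can be stable at week 8 and reach a partial response at week 16. Someone who paired Section 14.0 with the best-overall-response definition in Section 12.0 would count that patient. Someone who followed Section 9.3 would not.

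The thresholds are low enough for one patient to matter. Suppose none of the first 9 responds at the first scan and one responds later. One reading then stops the trial and the other continues it. Suppose instead that exactly 2 of 24 respond at the first scan, at least one of them among the first 9, and one more responds later. The final verdict then differs.

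Timing would differ as well. The 8-week count is complete once the ninth patient has had that scan. A count of 0 of 9 on best response is not final until all nine have progressed or left treatment. The plan says: "Given an expected accrual rate of 2 patients per month, the accrual to the phase 2 portion of the study" will take about 6 to 12 months. At that rate, 2 × (12/52) × 8 ≈ 3.7 patients would enrol in 8 weeks and 7.4 in 16 weeks, if accrual were not paused.

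**Working it through.** **Step 1. Does the design reproduce?** The inputs are all from Section 14.0: p0 = 5%, p1 = 25%, stage 1 of 9, stop at 0, second stage of 15, success at 3 or more of 24. With X1 ~ Bin(9, p) and X2 ~ Bin(15, p),

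P(success) = P(X1=1)·P(X2≥2) + P(X1=2)·P(X2≥1) + P(X1≥3).

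- p = 0.05: 0.2985 × 0.1710 + 0.0629 × 0.5367 + 0.0084 = 0.0931. P(0 of 9) = 0.95^9 = 0.630.
- p = 0.25: 0.2253 × 0.9198 + 0.3003 × 0.9866 + 0.3993 = 0.9028. P(0 of 9) = 0.75^9 = 0.075.

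The stated limits are 10% type I error and 90% power, and both are met. A grid search for the smallest expected sample size under the null returns this same design, with an expected sample size of 14.5. These figures hold for any binary response definition to which 5% and 25% refer.

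**Step 2. Which definition does the plan give?**

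| Place | Called the primary objective, outcome or endpoint? | Time point |
|---|---|---|
| Section 2.1 | yes | 8 weeks |
| Section 9.3 | yes | first 8-week response |
| Synopsis (1.0) | yes | none given |
| Section 14.0 | yes | none given |
| Section 12.0, best overall response | no | start of treatment to progression |

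Every time point attached to the primary outcome is 8 weeks. The untimed statements give less detail but do not conflict with it. The only passage that runs past week 8 is a RECIST category definition that is not called an endpoint and is not cited by the decision rules. Stage 1 can therefore be read when each of the first nine has had the 8-week scan or has left the study before it.

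**Step 3. What if the rates were any-time rates?** Let f be the share of first responses that come after week 8. The documents give no value, so f = 10%, 20% and 30% is an assumption. The rate counted at week 8 is then p(1 − f). Every 8-week responder is also an any-time responder, so the two readings disagree with a probability equal to the difference between their success (or stopping) probabilities.

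| f | Week-8 rate if any-time is 25% | Power, week 8 | Verdicts differ (0.9028 − power) | P(0 of 9), week 8 | Stage 1 differs (P − 0.0751) |
|---|---|---|---|---|---|
| 10% | 22.5% | 0.8616 | 4.1% | 0.1009 | 2.6% |
| 20% | 20.0% | 0.8047 | 9.8% | 0.1342 | 5.9% |
| 30% | 17.5% | 0.7280 | 17.5% | 0.1770 | 10.2% |

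If 5% is also an any-time rate, the week-8 count has a type I error of 7.3%, 5.5% and 4.0% for the same values of f. Following Section 9.3 does not push the type I error above 9.3% in these cases.

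**Step 4. Does the scan-window mismatch move the count?** The first assessment falls in weeks 7 to 9 under Section 12.0 and weeks 6 to 10 under footnote 6. Under the wider window the second falls in weeks 14 to 18. The intervals do not overlap, so a scheduled scan is attributed to the same assessment under either window.

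**The case for a change.** The strongest case for acting is that an endpoint should be stated once, in the section that holds the decision rules, when a single patient can reverse the decision. The two reversal cases described above need no assumption about how common late responses are. Nothing expressly says that 5% and 25% are 8-week rates, and the 29% used as a yardstick has no time point. There is also an opposite error. If 5% is the week-8 null and late responders were counted anyway, the chance of a positive result under the null would be 11.8%, 15.2% and 19.9% for f = 10%, 20% and 30%.

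Part of this stands. Section 14.0 is less complete than it should be, and the two scan windows disagree. The rest falls short. The inflated false-positive figures arise only if an analyst sets aside Section 9.3. The power figures need 25% to be an any-time rate, which the documents do not say. The plain reading is that a rate tested for the primary endpoint is a rate of that endpoint. The accrual figures assume enrolment runs on past nine patients, whereas Section 14.0 makes the further 15 conditional on at least one response. Whether to pause is a separate question from what counts as a response.

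**Conclusion.** The concern does not hold as a defect. Sections 2.1 and 9.3 fix the primary outcome as response at the first 8-week assessment, and Section 14.0 applies its rules to the primary endpoint. An analyst who reads the protocol as a whole counts CR plus PR at that scan, reads stage 1 when nine patients have reached it, and treats later first responses as descriptive. On that reading, with 5% and 25% taken as rates of the stated endpoint, type I error is 9.3% and power is 90.3%.

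The drop in power to between 86.2% and 72.8%, and the 4.1% to 17.5% of trials with differing verdicts, are hypothetical. They rest on an assumed late-response share of 10% to 30% and on 25% being an any-time rate. The two scan windows are a clerical inconsistency with no shown effect on any result. Carrying the time point into the synopsis and Section 14.0, and reconciling the windows, would be reasonable tidying at a future revision, but no change to the plan depends on it.

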10.0 EVALUATION DURING TREATMENT/INTERVENTION

Tables 10.1 outlines the schedule of assessments applied to patients. If the subject is unable to have a study assessment taken within the defined time window due to an event outside of his or her control (e.g. clinic closure, personal emergency, inclement weather, vacation) the assessment should be performed as close as possible to the required schedule. More frequent assessments should be obtained if clinically indicated. Subjects will return to the study site within 30 days after their last dose of trametinib and erlotinib to complete end of study assessments outlined below. Additional follow up will occur for subjects with AEs related to study treatment that are ongoing at the time of this visit and for subjects with SAEs related to study treatment that occur after the time of this visit.

Table 10.1: Study Calendar								
1 cycle=28 days	Screening	Cycle 1				Cycle 2	Cycle 3+	At progression/off study
	Within 4 weeks unless otherwise noted	C1D1	C1D7	C1D8	C1D15	C2D1	C3+D1	
Informed Consent	X							
Medical History	X	X		X	X	X	X	X
Concurrent Medication Reconciliation	X	X		X	X	X	X	X
Physical Exam/Performance status ¹	X	X			X	X	X	X
Ophthalmology Exam ²	X					X		
Vital Signs and Weight ¹	X	X			X	X	X	X
Complete Blood Count w/ differential ¹	X	X			X	X	X	X
Comprehensive Metabolic Panel (CMP) ^{1,3}	X	X			X	X	X	X
12 lead EKG ⁴	X	X				X	X	
Echocardiogram ⁵	X						X ⁵	
Adverse Events Evaluation ¹	X	X		X	X	X	X	X
Radiologic Tumor Assessments ⁶	X						X	X
MRI brain/disease assessment	X							
B-HCG ⁷	X							
Tumor Tissue ⁸	X							X
IMPACT Bloods ⁹	x							

¹Study Assessments (physical exams, vitals, weight, CBC, CMP, adverse events evaluation) will be repeated C1D1, C1D8, C1D15 (first cycle), then monthly subsequently. C1 assessments have a window of +/- 3 days, C2 onward assessments have a window of +/- 2 weeks.

²Baseline Ophthalmic exam will include visual acuity, visual field examination, tonometry, slit lamp biomicroscopy of the anterior segment (with special attention to inflammation) and the posterior segment, and indirect fundoscopic examination with special attention to possible retinal abnormalities. Exams are required at screening, month 1 +/- 2 week, and month 6 +/- 4 weeks. Additional ophthalmic exams will be performed if symptomatically warranted.

³CMP includes glucose, blood urea nitrogen, creatinine, sodium, potassium, chloride, bicarbonate, calcium, total protein, albumin, serum bilirubin, alkaline phosphatase, ALT, AST

⁴A single 12 lead ECG should be performed at screening and day 1 of every cycle +/- 2 weeks.

⁵Echocardiogram should be performed at screening and every three cycles +/- 2 weeks

⁶Response to therapy will be assessed by interval imaging studies every 2 cycles (8 weeks)+/- 2 weeks with response evaluated using RECIST version 1.1. Radiologic imaging will include a CT chest +/- abdomen/pelvis depending on sites of disease with or without contrast. If an appropriate imaging study is performed early for any reason (i.e. hospitalization), it can be used for disease assessment. CT scans should be completed if the patient comes off study for any reason other than progression. If a CT scan was completed within the last 8 weeks, it will not need to be repeated.

⁷ B-HCG testing (serum or urine) should be performed only in women of child bearing potential.

⁸ Tumor biopsy will be performed within 3 months of study initiation (unless archived tissue is available from a biopsy obtained after progression on erlotinib) and at time of progression +/- 4 weeks. Both patients on the phase 1 and phase 2 portion of the study will have biopsies performed.

⁹ IMPACT bloods will be drawn at screening for next-generation sequencing based testing.

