11.3.6 Visual Changes

Episodes of visual changes have been observed in patients receiving trametinib. The causal relationship between a change in vision and the study treatment should be carefully explored and an ophthalmologist should be consulted. Patients are required to have a standard ophthalmic exam performed by an ophthalmologist at baseline and as clinically warranted. The exam will include indirect fundoscopic examination, visual acuity (corrected), visual field examination, tonometry, and direct funduscopy. Special attention should be given to retinal (e.g., CSR) or retinal vein abnormalities (e.g., RVO).

Guidelines regarding event management and dose reduction for visual changes considered to be related to study treatment are provided in the table below.

Management and Trametinib Dose Modification for Visual Changes		
Event CTCAE Grade	Management Guideline	Dose Modification
Any grade of CRS or RVO should be reported as SAE		
Grade 1 Asymptomatic or symptomatic but not limiting ADL; intervention not indicated.	
 • Consult ophthalmologist within 7 days of onset. • Exclude CSR or RVO. • Consult retinal specialist if available in case of CSR or RVO. • Continue follow up examination(s) (by retinal specialist if available) for CSR and RVO. 	
 • Continue trametinib at the same dose level until ophthalmologic examination can be conducted.* • If ophthalmologic examination cannot be performed within 7 days of onset, interrupt trametinib until CSR and RVO can be excluded and symptoms resolve. • If CSR and RVO excluded restart trametinib at same dose level. • If CSR: Interrupt trametinib until symptoms resolve and exam (by retinal specialist if available) shows resolution. May restart trametinib with one dose level reduction. • If RVO: Permanently discontinue trametinib.

Management and Trametinib Dose Modification for Visual Changes		
Event		
CTCAE Grade	Management Guideline	Dose Modification
Any grade of CRS or RVO should be reported as SAE		

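### The two-week window around the cycle 2 day 1 checks and the month-1 eye exam fits the 28-day DLT period poorly, so a silent DLT in the run-in may be seen late or be impossible to date (minor)

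*Combined protocol and SAP*

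**What the plan says.** Section 9.3 observes run-in patients for DLTs over one 28-day cycle. Section 14.0 defines a DLT as a listed toxicity "that occurs within one cycle after initiation of treatment with erlotinib and trametinib". With 0 or 1 DLT in six patients, phase 2 uses dose level 0; with 2 or more it uses dose level -1.

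Several DLTs in section 9.4 can occur without symptoms: grade 3 or higher "AST, ALT, alkaline phosphatase or total bilirubin", grade 4 thrombocytopenia, grade 4 anemia, and central serous retinopathy (CSR) or retinal vein occlusion (RVO), the last two with no grade or symptom requirement.

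Footnote 1 to Table 10.1 places the exam, CBC and CMP at C1D1, C1D8 and C1D15, then monthly, and states: "C1 assessments have a window of +/- 3 days, C2 onward assessments have a window of +/- 2 weeks". Footnote 2 covers the eye: "Exams are required at screening, month 1 +/- 2 week, and month 6 +/- 4 weeks". Footnote 4 gives the ECG on day 1 of each cycle the same two-week tolerance.

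Beyond the calendar, section 10.0 asks for more frequent assessments when clinically indicated. Footnote 2 adds that "Additional ophthalmic exams will be performed if symptomatically warranted", and section 11.3.6 says "Patients are required to have a standard ophthalmic exam performed by an ophthalmologist at baseline and as clinically warranted". No section sets a narrower window for run-in patients, names results that must be available before the dose decision, or says how to date an abnormality first found after day 28.

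**The concern.** The checks that close the DLT period carry a tolerance of two weeks either way around a period only four weeks long. Symptomatic events will bring the patient in. Silent ones depend on scheduled tests, and the clauses on extra assessments respond to clinical signals.

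A silent event can go wrong in three ways. It may still be present at a late visit but not be datable to before or after day 28, so it could be misclassified in either direction. It may arise and resolve before a late visit. Or, if the visit is held very early, it may arise after the check.

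The decision turns on a single event: if the true count is two, one uncounted DLT sends phase 2 to dose level 0. Section 3.0 says this combination was not tested in the earlier phase 1 study. Up to 18 further patients (24 less the six carried forward) would receive it.

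**Working it through.** **Inputs.** DLT period: days 1-28 (sections 9.3 and 14.0). Windows: 3 days either way in cycle 1 and 14 days from cycle 2 (Table 10.1, footnote 1); the eye exam and ECG also have 14 days (footnotes 2 and 4). C1D1 is day 1, so C2D1 is day 29. Assumption: month 1 for the eye exam means day 29, because the table marks it in the C2D1 column.

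**Permitted days.**
- C1D15: 15 ± 3 = days 12-18.
- C2D1 exam, labs, ECG and eye exam: 29 ± 14 = days 15-43.
- Latest check relative to the end of the period: 43 - 28 = 15 days after.
- Earliest check: 28 - 15 = 13 days before. This would coincide with the nominal C1D15 visit and is unlikely.

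**Dating a finding first seen at C2D1.** Suppose the C1D15 labs, drawn on day 15, were normal. Onset then lies between day 16 and the day of the check.

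| C2D1 held on | Possible onset days within the period | Possible onset days after it |
|---|---|---|
| Day 29 (nominal) | 28 - 15 = 13 | 29 - 28 = 1 |
| Day 43 (latest) | 13 | 43 - 28 = 15 |
| Days 28-31 (proposed) | 13 | 0 to 3 |

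For the eye there is no earlier on-treatment exam. A day-43 finding could have begun on any of 28 days inside the period or 15 after it; with the exam on days 28-31, at most 3 days lie after it.

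**Longest interval between C1D15 and C2D1 labs.** Plan: 43 - 12 = 31 days, which needs both visits at opposite extremes. Nominal: 29 - 15 = 14. Proposed: 31 - 12 = 19.

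**What the window does not cause.** Whenever C2D1 falls after day 28, the last scheduled labs inside the period are those of C1D15, which leaves 28 - 18 = 10 to 28 - 12 = 16 days without a draw. That holds equally on day 29 and on day 43. It comes from having no visit between C1D15 and C2D1.

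**Illustration of size (assumed rates).** Take symptomatic DLTs at 3/22 = 13.6%, the pooled rate in the earlier phase 1 study across its dose levels (section 3.0), and suppose all are counted. Add a silent DLT rate s, of which a share l is lost because of the window. With q = 0.136 + s(1 - l), the chance of 0-1 counted DLTs in six is (1 - q)^6 + 6q(1 - q)^5.

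| s | l | Nothing lost | Share l lost | Change |
|---|---|---|---|---|
| 2% | 10% | 0.761 | 0.766 | +0.005 |
| 2% | 50% | 0.761 | 0.785 | +0.02 |
| 10% | 25% | 0.567 | 0.628 | +0.06 |
| 10% | 50% | 0.567 | 0.689 | +0.12 |

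The documents support neither s nor l. The table shows direction and rough scale only, and only for lost events; misdated events could move the count either way.

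**The case against.** A window is a tolerance around a scheduled day, not a plan to use its limits. A visit near day 29 closes the period well. Patients must be observed for a full cycle, and section 13.0 replaces run-in patients who leave before completing one for reasons other than a DLT, so a dose decision with no end-of-cycle assessment would sit badly with the plan. All three DLTs in the earlier phase 1 study were diarrhea or mucositis, which patients report. This stands, and it is why the effect is probably small. It does not reach silent events, and no specific result is required before the decision.

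Four stronger readings are tempting and are not supported:

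- A reader might infer that the window leaves the last 10-16 days of the period unmonitored. As shown above, the visit schedule does that.
- A reader might infer a large shift in the dose decision. With a true DLT rate of 33%, the chance of 0-1 counted DLTs rises from 0.36 to 0.74 if half of all DLTs go uncounted, but that would include the symptomatic events that the plan does pick up.
- A reader might count permitted days and conclude that most visits will be mistimed. The documents do not say when visits occur.
- A reader might add QTc prolongation to the silent DLTs. Section 9.4 does not name it; it would count only under the general clause on other grade 3 or higher major organ toxicity.

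For the eye, moving the exam earlier still misses an event that appears and clears before it. The gain there is mainly in dating.

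**Conclusion.** The point holds as a minor one. The stated tolerance fits the 28-day endpoint poorly: a silent DLT may be first seen up to 15 days after the period and be undatable, or may clear before a late visit. The risk that one arises after a very early visit is remote. This rests on the window being used in practice, on month 1 meaning day 29, and on silent DLTs occurring at all. The documents say nothing about how often, so the change in the dose decision cannot be estimated from them. Lost events favor dose level 0; undatable ones can err either way.

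**What to change.** For run-in patients only, hold the planned C2D1 exam, CBC, CMP and ECG and the first on-treatment eye exam on days 28-31, and make the phase 2 dose decision only after these results are in for all run-in patients. Days 28-31 are preferable to day 28 ± 3, which would still permit a check on day 25 and leave three days of the period after it.

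The cost is a change to the calendar wording, tighter scheduling of one planned visit and one planned eye exam in up to six patients, and a short wait before the dose decision. No test or visit is added. Ascertainment is still incomplete: up to 19 days can separate the C1D15 and C2D1 labs, and a single CBC cannot establish "Grade=4 neutropenia lasting >5 days".
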